8.5.4 Triheptanoin-Naïve Cohort: Statistical Comparisons in Efficacy Endpoints

For UX007/trihep naïve subjects, additional analyses will be conducted to assess the effects of UX007 by comparing post-UX007 assessments with baseline assessment via statistical tests.

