The continued effects of UX007 treatment on clinical and physiologic disease of the skeletal muscle, the liver and the heart will be assessed. Creatine kinase (CK) will be measured as a biomarker of skeletal myopathy. The metabolic effects on the liver and energy homeostasis will be assessed by evaluating liver enzymes and serum glucose as biomarkers. Cardiac disease will be assessed by annual echocardiograms (ECHO).

The impact of UX007 treatment on major clinical events will also be assessed throughout the study. Major events are defined as musculoskeletal, hepatic, and cardiac events caused by LC-FAOD, or intercurrent illness complicated by LC-FAOD, resulting in any hospitalization, ER visit, or emergency intervention (any unscheduled administration of therapeutics at home or in the clinic). In subjects for which prior medical events data have already been collected during a prior UX007 protocol the effect of UX007 treatment on major clinical events during this study will be compared with the subject's available historical information for the

18-24 months prior to beginning UX007 (or from birth for subjects less than 18 months of age). For subjects who are treatment naïve, available historical event data will be collected prior to UX007 administration. The event rate per year during UX007 treatment will be compared with the subject's available historical information for the 18-24 months prior to beginning UX007 (or from birth for subjects less than 18 months of age). Dosing compliance and diet will be regularly monitored along with a standard panel of safety assessments. Figure 7.1.1 provides a schematic of the study design.

* A safety follow-up call will be completed 30-35 days after the last dose of study drug

A PK sub-study will evaluate the steady-state PK of UX007 and UX007 metabolites in a minimum of 12 patients with LC-FAOD. Subjects enrolled in the sub-study will have serial PK samples collected.

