7.2 Discussion of Study Design, Including Choice of Control Group

The primary objective of this open-label Phase 2 extension study is to evaluate the long-term safety and efficacy of UX007 in patients with LC-FAOD. The study will also explore long-term effects of UX007 on energy metabolism and clinical events associated with LC-FAOD. Evaluations of biomarkers will also be performed to provide supportive evidence and potentially confirm surrogate endpoints of efficacy. LC-FAOD laboratory measures may potentially provide supportive evidence of effects on energy metabolism and safety.

The sample size is intended to provide the maximum amount of information regarding UX007 long-term safety and efficacy in a diverse LC-FAOD population. Since all subjects will receive the same investigational product, randomization and blinding are unnecessary; study drug will be provided open-label.

Any historical data obtained from medical records will be used as a comparator for the Treatment Extension Period, enabling those subjects to represent an internal control for assessment of efficacy. While the lack of a parallel control group may introduce difficulties in discerning natural disease progression from treatment effectiveness, a placebo -controlled study of this duration is difficult to conduct and possibly not ethical given the need for ongoing disease management, and the potential for acute, life-threatening crises in untreated patients.

Given the acute-on-chronic nature of LC-FAOD, subjects will be eligible to continue maintenance UX007 treatment for up to 7 years (84 months) or until commercial availability of UX007 in any region, whichever occurs first. The treatment duration is intended to provide additional long-term safety information and provide sufficient insight on sustained clinical effects in LC-FAOD patients under a single study protocol.

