7.3 Selection of Study Population

The study will be conducted in approximately 150 subjects who have participated in clinical studies or compassionate use programs with UX007/triheptanoin, or who have failed conventional therapy and have documented clear unmet need (in the opinion of the Investigator and Sponsor). Most subjects in this study will have prior treatment exposure to UX007/triheptanoin, although it is possible to enroll treatment-naïve individuals if prior study participation involved assignment to a control treatment arm.

The inclusion criteria are structured to enroll subjects with various types of LC-FAOD (CPT-I, CPT-II, VLCAD, LCHAD, TFP, or CACT deficiencies).

Many LC-FAOD patients are seriously impacted by their disorder from birth. Triheptanoin has been administered previously to LC-FAOD patients, including newborns, infants, children, and adults. The experience reported in clinical studies and compassionate use programs suggests a favorable risk/benefit profile for the target study population. The Sponsor has taken all reasonable measures to ensure the protection and safety of this population. Appropriate pediatric expertise will be available at all trial sites, and efforts will be focused on minimizing risk, fear, pain and distress for this population during conduct of the study.

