7.3.1 Inclusion Criteria

Individuals eligible to participate in this study must meet all of the following criteria:

- 1. Male or female, 6 months of age or older
- 2. Prior participation in a clinical study assessing UX007/triheptanoin treatment for LC-FAOD. Study Sponsors/Collaborators include: Oregon Health & Science University, University of Pittsburgh, and Ultragenyx Pharmaceutical (ClinicalTrials.gov Identifiers: NCT01379625, NCT01461304, and NCT01886378). Patients who received UX007/triheptanoin treatment as part of other clinical studies; investigator sponsored trials (IST); expanded access/compassionate use treatment programs; or patients who are treatment naïve (i.e., naïve to both UX007 and food-grade triheptanoin), have failed conventional therapy and, in the opinion of the Investigator and Sponsor, have documented clear unmet need, may also be eligible at the discretion of the Sponsor.
- 3. Confirmed diagnosis of LC-FAOD including: carnitine palmitoyltransferase (CPT I or CPT II) deficiency, very long chain acyl-CoA dehydrogenase (VLCAD) deficiency, long chain 3-hydroxy-acyl-CoA dehydrogenase (LCHAD) deficiency, trifunctional protein (TFP) deficiency, or carnitine-acylcarnitine translocase (CACT) deficiency. Information

on diagnosis will be obtained from medical records and should include confirmed diagnosis by results of acylcarnitine profiles, fatty acid oxidation probe studies in cultured fibroblasts, and/or mutation analysis.

- 4. Willing and able to complete all aspects of the study through the end of the study, including visits and tests, documentation of symptoms and diet, and administration of study medications. If a minor, have a caregiver(s) willing and able to assist in all applicable study requirements.
- 5. Provide written informed consent (subjects aged ≥ 18 years), or provide written assent (where appropriate) and have a legally authorized representative willing and able to provide written informed consent, after the nature of the study has been explained and prior to any research-related procedures.

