3.1 Study Population

The study is designed to obtain long-term safety information and evaluate maintenance of efficacy in a diverse LC-FAOD population.

The study will be conducted in approximately 100 subjects who have participated in clinical studies or compassionate use programs with UX007/triheptanoin, or who have failed conventional therapy and have documented severe unmet need (in the opinion of the investigator and sponsor). Most subjects in this study will have prior treatment exposure to UX007/triheptanoin, although it is possible to enroll treatment-naïve individuals if prior study participation involved assignment to a control treatment arm.

The inclusion criteria are structured to enroll subjects with various types of LC-FAOD (CPT-I, CPT-II, VLCAD, LCHAD, TFP, or CACT deficiencies). Refer to the protocol for detailed inclusion and exclusion criteria.

Subjects in this study are to meet one or more of the following requirements:

- Participated in the UX007-CL201 study (ClinicalTrials.gov Identifier: NCT01886378)
- Previously enrolled in another UX007/triheptanoin study.
 - Study Sponsors/Collaborators include: Oregon Health & Science University (referenced as OHSU)
 - University of Pittsburgh (referenced as CompUse; ClinicalTrials.gov Identifiers: NCT01379625 and NCT01461304).
 - Participated in the UX007-CL001 study
 - Received UX007/triheptanoin treatment as part of other clinical studies; investigator sponsored trials (IST); expanded access/compassionate use treatment programs; eIND.
- Are treatment naïve (i.e., naïve to both UX007 and food-grade triheptanoin), have failed conventional therapy and, in the opinion of the investigator and sponsor, have documented severe unmet need, may also be eligible at the discretion of the sponsor.

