5.6 Subject Cohorts for Presentation

All CL202 subjects will be classified into one of the three non-overlapping cohorts in analysis presentations:

- UX007/trihep naïve subjects. This cohort consists of subjects who had no prior exposure to UX007/trihep before enrolling into CL202. However if a subject participated in a prior UX007/trihep study but was off UX007/trihep for more than two years before enrolling into this study, then this subject will be treated as a naïve subject and historical major clinical events will be collected.
- UX007-CL201 rollover subjects. This cohort consists of subjects who rolled over from UX007-CL201 to UX007-CL202 study.
- Other. This cohort includes subjects unassigned to the above two cohorts, i.e., subjects from [name] Comp sites, OHSU site, eIND program and etc.

A subject may have participated in more than one prior UX007/trihep studies/programs, and the cohort that the subject will be assigned to is determined based on the following priority order: UX007-CL201 rollover subjects and Other.

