8.5.4.1 Pre- and Post-UX007 Comparisons in MCE in Triheptanoin-Naïve Cohort

All MCE related endpoints (i.e., annualized event/duration rates of MCE overall and by event type) will be analyzed by comparing pre- and post-UX007 treatment period. The pre-UX007 treatment period for UX007/trihep naïve subjects corresponds to the retrospective MCE collection period, i.e., study period 3.

The 18 months pre-UX007 treatment period will be compared to the 18 months post-UX007 treatment period using the paired t-test. The Wilcoxon signed rank test will be performed as a nonparametric alternative to the paired t-test when the normality assumption is questionable. For subjects who had longer than 18 months of follow up on study as of the data cutoff date, MCEs that occurred between UX007 initiation and 18 months post UX007 initiation will be

included for calculating number of MCEs and total durations in days of MCEs will be calculated accordingly. For subjects who terminated the study prior to reaching 18 months on study, MCEs that occurred between UX007 initiation and the termination visit will be included for calculating number of MCEs and total durations in days of MCEs will be calculated accordingly. For historical annualized event rate and annualized duration rate observed during study period 3, the data collection period is 18 months (548 days) preceding the date of UX007 initiation. For subject's age less than 18 months at UX007 initiation, the data collection period will be between the birthdate and the date prior to UX007 initiation.

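### If recent events prompted a naive subject's entry, regression to the mean inflates the 18-month pre/post MCE comparison, and no planned sensitivity analysis changes the reference window

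*SAP*

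**What the plan says.** Protocol 7.3.1 admits treatment-naive patients who "have failed conventional therapy and, in the opinion of the Investigator and Sponsor, have documented clear unmet need". SAP 3.1 describes the same route with the word severe: "have documented severe unmet need, may also be eligible at the discretion of the sponsor". Neither gives a number of events or a look-back period.

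For this cohort, SAP 8.5.4 announces that "additional analyses will be conducted to assess the effects of UX007 by comparing post-UX007 assessments with baseline assessment". SAP 5.10.3 sets the retrospective period as the 548 days ending the day before UX007 treatment day 1. For subjects younger than 18 months at initiation, SAP 8.5.4.1 uses the time since birth. The same section states: "The 18 months pre-UX007 treatment period will be compared to the 18 months post-UX007 treatment period using the paired t-test". The Wilcoxon signed rank test is the fallback. SAP 8.1 makes tests two-sided at 0.05, and SAP 3.9 presents these subjects as their own control for efficacy.

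The sensitivity analyses in SAP 8.5.4.2 are a negative binomial model, removal of outliers, and laboratory-threshold definitions of rhabdomyolysis and hypoglycemia events. SAP 8.4.1 adds individual profile figures that show MCEs across both periods. Protocol 7.2 concedes a limit of the design, "While the lack of a parallel control group may introduce difficulties in discerning natural disease progression from treatment effectiveness", but does not name regression to the mean and plans no analysis for it.

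**The concern.** Eligibility is judged at enrolment, and the reference period runs up to the first dose. If a recent run of events is what documented unmet need, that run is counted in the reference rate. Such runs are partly chance, so the rate afterwards would drift back toward the subject's usual level without any drug effect. The paired test would attribute the whole fall to UX007.

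At stake is how a significant reduction in the naive cohort is read. It is this cohort's tested comparison of MCE rates before and after UX007, and SAP version 2.0 added sensitivity analyses to show that the MCE findings are robust. None of them addresses this threat.

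**Working it through.** **The plan's own figure.** The only checkable number is the window: 18 × 30.4375 = 547.875 days, which rounds to the stated 548. The documents give no event rate, between-subject variation, naive-cohort size or expected reduction, so the size of the bias can only be shown under assumptions.

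**Inputs.** From the SAP: 1.5 years before and 1.5 years after first dose. Assumed: no drug effect; a constant true rate per subject, gamma-distributed with mean μ = 1 or 2 MCEs per year; shape k = 2, 1 or 0.5 (CV = 1/√k = 0.71, 1 or 1.41); Poisson counts; every subject entered after at least one MCE in the last w years.

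**Formulas.**
- Chance of no event in the look-back: P0 = (1 + μw/k)^(−k)
- Mean true rate of those selected, which is the expected post rate: m = μ[1 − (1 + μw/k)^(−(k+1))] / (1 − P0)
- Mean events in the look-back of those selected: c = μw / (1 − P0)
- Pre rate = [c + (1.5 − w)m] / 1.5
- Spurious reduction = 1 − m / pre rate

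**Worked case** (μ = 1, k = 1, w = 0.5). P0 = 1/1.5 = 0.667; m = (1 − 0.444)/0.333 = 1.667; c = 0.5/0.333 = 1.5; pre rate = (1.5 + 1.667)/1.5 = 2.111; reduction = 1 − 1.667/2.111 = 21%.

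**Full 18-month reference:**

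| Look-back | μ | k = 2 | k = 1 | k = 0.5 |
|---|---|---|---|---|
| 3 months | 1 | 28.2% | 22.9% | 16.6% |
| 3 months | 2 | 14.9% | 11.8% | 8.4% |
| 6 months | 1 | 25.9% | 21.1% | 15.4% |
| 6 months | 2 | 12.3% | 10.0% | 7.4% |

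Simulation of the same model gave 7% to 29%.

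**Dilution.** If only half the cohort is selected this way and the rest have the mean rate of 1 (μ = 1, k = 1, w = 0.5), post = (1.667 + 1)/2 = 1.333, pre = (2.111 + 1)/2 = 1.556, and the reduction is 14% instead of 21%.

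**Do the planned checks detect it?** Simulated with entry on one MCE in the last 6 months, for (μ, k) = (1, 1), (2, 1) and (2, 2):
- Removing outliers by the SAP's 1.5 × IQR rule moves the spurious reduction from 21%, 10% and 12% to 21%, 13% and 17%.
- A rate ratio on the same periods is 0.79, 0.90 and 0.88, where the truth is 1.00.
- Successive 18-month on-treatment intervals differ by 0%, so the on-treatment trend cannot show the bias.

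**Dropping the last 6 months.** If w ≤ 0.5, months −18 to −6 contain none of the selection window; their expected rate is m and the spurious reduction is 0. If w > 0.5, the reference rate over the remaining year is c(w − 0.5)/w + (1.5 − w)m. For μ = 1, k = 1, w = 1: P0 = 0.5, m = 0.75/0.5 = 1.5, c = 2. The full window gives (2 + 0.75)/1.5 = 1.833, a reduction of 18%. The shortened window gives 1 + 0.75 = 1.75, a reduction of 14%. With months −24 to −6 it is (1 + 1.5)/1.5 = 1.667, a reduction of 10%.

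Over the same grid, months −18 to −6 leave 4.7% to 17.4% for a 12-month look-back and 5.4% to 18.7% for 18 months, so about 5% to 19%. When entry required at least two events anywhere in the 18 months, simulation left 10% to 23%, unchanged by the exclusion.

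**The case against.** The strongest objection is that the premise is an inference. A reader might say that these subjects are tested against the very months that qualified them. The documents do not say so: the criterion names no MCEs, count or period. Long-standing treatment failure with a stable high rate would satisfy it and would leave little regression to the mean. This stands, and it makes the point conditional.

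The cohort is also mixed. Protocol 7.3 notes that "it is possible to enroll treatment-naïve individuals if prior study participation involved assignment to a control treatment arm", and SAP 5.6 counts as naive a prior-study participant who "was off UX007/trihep for more than two years before enrolling into this study". Neither route requires recent events. This stands too: the 7% to 28% range describes a fully selected cohort.

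A reader might also infer that nothing in the plan could reveal the problem. That goes too far. The SAP 8.4.1 profile figures could show events clustering before initiation. They do not estimate the bias or correct the test.

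Finally, the comparison is an additional analysis in a mostly descriptive plan. That limits the consequence. SAP 8.5 nevertheless says that efficacy in this cohort will be assessed by this comparison.

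**Conclusion.** The point holds in conditional form. Need-based entry, a reference window ending the day before first dose, a within-subject test at 0.05, and sensitivity analyses that all retain that window are all in the documents. How far recent events drove entry is not.

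Under the assumed rates and with every subject selected on an MCE in the last 3 to 6 months, selection alone produces a reduction of about 7% to 28%. Mixed routes or a stable high rate make it smaller.

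It would be wrong to conclude that the primary efficacy result is biased: SAP 8.5.1 and Table 11.1.1 make it a descriptive summary of study period 1 in the full analysis set. Nor does the calculation show that an observed reduction in the naive cohort is spurious. It shows that part of one could be, and that the plan has no estimate of how much. This is an improvement that should be made, not a defect that invalidates the plan.

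**What to change.** Add two items to SAP 8.5.4.2 and leave the main analysis unchanged.

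(a) Tabulate the MCE rate by 6-month block before UX007. A rise in the last block or blocks would suggest selection on recent events; a flat profile would support the sponsor's reading.

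(b) Repeat the pre/post comparison without the last 6 months before UX007, annualizing to the remaining window. Use months −24 to −18 only where they were actually collected: Protocol 7.1 and SAP 3.9 speak of 18–24 months of history, but SAP 5.10.3 defines 548 days.

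Restrict (b) to subjects with a stated minimum of remaining history, for example 6 months. Report how many subjects are dropped, and show the full-window result in the same subset. The loss falls mainly on infants: entry is allowed from 6 months of age, so a subject starting then has no reference period left, and one starting at 9 months has about 3 months. A 6-month minimum requires age 6 + 6 = 12 months at first dose.

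State in the SAP that (b) removes the bias only if selection looked back 6 months or less, and that about 5% to 19% can remain for look-backs of 12 to 18 months. A reduction that persists in (b) therefore does not by itself rule out regression to the mean.

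The cost is one table and one sensitivity analysis. No new data are needed, because assigning events to the retrospective period already requires their dates. The pre-period in (b) falls from 18 to 12 months where no earlier history exists, so the Poisson variance of its annualized rate rises by 1.5/1.0 = 1.5 times. That loss, and the loss of some infants, is confined to the sensitivity analysis.

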8.5.4.1 Pre- and Post-UX007 Comparisons in MCE in Triheptanoin-Naïve Cohort

All MCE related endpoints (i.e., annualized event/duration rates of MCE overall and by event type) will be analyzed by comparing pre- and post-UX007 treatment period. The pre-UX007 treatment period for UX007/trihep naïve subjects corresponds to the retrospective MCE collection period, i.e., study period 3.

The 18 months pre-UX007 treatment period will be compared to the 18 months post-UX007 treatment period using the paired t-test. The Wilcoxon signed rank test will be performed as a nonparametric alternative to the paired t-test when the normality assumption is questionable. For subjects who had longer than 18 months of follow up on study as of the data cutoff date, MCEs that occurred between UX007 initiation and 18 months post UX007 initiation will be

included for calculating number of MCEs and total durations in days of MCEs will be calculated accordingly. For subjects who terminated the study prior to reaching 18 months on study, MCEs that occurred between UX007 initiation and the termination visit will be included for calculating number of MCEs and total durations in days of MCEs will be calculated accordingly. For historical annualized event rate and annualized duration rate observed during study period 3, the data collection period is 18 months (548 days) preceding the date of UX007 initiation. For subject's age less than 18 months at UX007 initiation, the data collection period will be between the birthdate and the date prior to UX007 initiation.

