5.5 Study Days

Study days of an event/assessment is defined as the date of the event/assessment minus the date of Study Day 1. If the result is a positive number or zero, add one day.

All derivations of duration are initially done based on days and converted to weeks, months and years if needed using 7, 30.4375 and 365.25, respectively, as denominator, if not otherwise specified.

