5.10.1 Study Period 1 (Main Study Period)

Study period 1, or the main study period, starts from study day 1 till the last visit day in CL202. The last visit date is the last date among the early termination visit date, the study completion visit date, the safety follow up visit date, or the last visit date as of a clinical cutoff date, if applicable. Study period 1 will be used for all efficacy on FAS and safety analyses unless otherwise specified.

5.10.2 Study Period 2

Study period 2 has the same ending date as Study period 1 but starts from UX007 treatment day 1. Study period 2 will be used in select analyses for UX007-CL201 rollover subjects.

[figure not shown]
5.10.3 Study Period 3

Study period 3 starts from the 18 months (548 days) preceding UX007 treatment day 1 and ends 1 day prior to UX007 treatment Day 1. Study Period 3 is referred as the retrospective period for MCE data collection.

Study period 3 will be used for UX007-CL201 rollover subjects and UX007/trihep naïve subjects only in select analyses.

The following figure illustrates the definitions of the three study periods.

Figure 5.10.3.1: Diagram of Study Periods in CL202

Study Period 1 is defined for all enrolled subjects in CL202; Study Period 2 is defined for CL201 rollover subjects only; Study Period 3 is defined for CL201 rollover subjects and UX007/trihep naïve subjects. CL201 treatment period exists for CL201 subjects only;

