5.11 Annualized Event Rate

The numbers of MCE will be annualized for each subject using the following formula:

$$\text{Annualized Event Rate} = \frac{\text{Number of events}}{\text{Duration of data collection period in days}/365.25}$$

The number of MCEs will be derived as the total number of events as recorded in the major clinical event CRF that occurred during the specific data collection period. Whenever an annualized rate is calculated over study period 1, the number of days is calculated from study day 1 till the data cutoff date or the early termination/study completion visit date for subjects who have early terminated/completed the study.

Annualized event rates will be calculated for MCEs overall and for each event type (ie., rhabdomyolysis, hypoglycemia, and cardiomyopathy respectively).

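### For subjects aged 18 months or more, the pre-UX007 event rate is divided by a fixed 548 days even if the records cover less, which understates that rate wherever history is short

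*SAP*

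**What the plan says.** SAP 8.5.4.1 and 8.5.5.1 use the same rule for the historical rates: "the data collection period is 18 months (548 days) preceding the date of UX007 initiation". SAP 5.10.3 defines the period in the same way: "Study period 3 starts from the 18 months (548 days) preceding UX007 treatment day 1". The sentence after the rule in both analysis sections makes one exception, for infants, whose period ends the day before treatment starts: "For subject's age less than 18 months at UX007 initiation, the data collection period will be between the birthdate and the date prior to UX007".

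SAP 5.11 sets the rate denominator as "Duration of data collection period in days", divided by 365.25. The numerator is the "total number of events as recorded in the major clinical event CRF that occurred during the specific data collection period". SAP 5.12 uses the same days for the duration rates.

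Protocol 7.1 is looser about what history will exist: "For subjects who are treatment naïve, available historical event data will be collected prior to UX007 administration". The target look-back is 18 to 24 months, or from birth for the youngest subjects, with no minimum length of records. SAP 3.9 repeats the 18-to-24-month target without the qualification about availability. SAP 7.2.4 deals with a missing study exit date but has no rule for an incomplete look-back.

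In the negative binomial sensitivity analysis, SAP 8.5.4.2.1 names time in study period 1 as the offset. SAP 8.5.5.2.1 names the time the subject stays in the study. Neither names an exposure for the pre-UX007 row.

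**The concern.** A rate needs a denominator that matches the time over which events could have been recorded. With a fixed 548 days, a stretch with no records counts as observed and event-free. The SAP accepts the principle for infants, whose denominator is cut to time since birth, but does not extend it to older subjects whose records start late.

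There is no parallel control group. SAP 3.9 makes the subject's own history the internal control, and SAP 8.5 assesses efficacy on MCE endpoints in naïve subjects by comparing rates before and after UX007. In the naïve cohort this is done by paired t-test or Wilcoxon signed rank test at two-sided 0.05. If the pre-UX007 rate is too low for some subjects, the estimated change depends on record completeness as well as on treatment, and a real reduction could be missed. The same error would enter the duration rates and the rates by event type.

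**Working it through.** **Inputs.** Window of 548 days (SAP 8.5.4.1, 8.5.5.1, 5.10.3). Rate = events / (days/365.25) (SAP 5.11). Months and years are 30.4375 and 365.25 days (SAP 5.5). Record coverage is not given in either document, so the coverage values below are assumptions.

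**The plan's own figure.** 18 × 30.4375 = 547.875, which rounds to 548. It reproduces.

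**One subject.** If records cover d of the 548 days and the event rate is constant over the window, the expected pre rate is the true rate × d/548. For a subject aged 18 months or more with 3 recorded events, the fixed rule gives 3/(548/365.25) = 2.0 per year whatever the coverage.

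| Months covered | Days d | d/548 | Rate on covered days (per year) |
|---|---|---|---|
| 18 | 547.9 | 1.00 | 2.0 |
| 15 | 456.6 | 0.83 | 2.4 |
| 12 | 365.2 | 0.67 | 3.0 |
| 9 | 273.9 | 0.50 | 4.0 |
| 6 | 182.6 | 0.33 | 6.0 |

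The paired test works on differences. Take the 12-month subject with a true pre rate of 3.0 and a post rate half of that, 1.5. The true change is 1.5 − 3.0 = −1.5 per year; the fixed rule gives 1.5 − 2.0 = −0.5.

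**Infant check.** A 9-month-old with 3 events gets 3/(273.9/365.25) = 4.0 per year under the existing exception, so nothing changes for that subject.

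**Cohort mean.** If a share f of subjects has d days of records and true rates are equal across subjects, the mean pre rate is multiplied by k = 1 − f(1 − d/548). A true post/pre ratio of 0.50 then appears as 0.50/k.

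| Coverage in the short-record share | f = 10% | f = 25% | f = 50% |
|---|---|---|---|
| 15 months | 0.508 | 0.522 | 0.546 |
| 12 months | 0.517 | 0.545 | 0.600 |
| 6 months | 0.536 | 0.600 | 0.750 |

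With f = 0 the ratio stays at 0.50.

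**Negative binomial model.** A model with a pre row and a post row for each subject needs an exposure for each row. The stated offset describes on-study time only, so as written it supplies neither 548 days nor covered days for the pre row.

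**The case against.** The strongest reply is that the documents do not show a single subject aged 18 months or more with short records. SAP 3.9 plans for 18 to 24 months of history, and the 548-day window is the lower end of that range. Collecting what is available does not by itself mean partial coverage. For the rollovers, the protocol describes the history as already collected under an earlier protocol. Protocol 5.2.3 reports that CL201 used a 78-week pre-treatment period, and 78 × 7 = 546 days is essentially the same window. All of this stands: it makes the bias conditional, and less likely in the rollover cohort. It does not supply a rule for short records.

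A reader might infer that every historical count is divided by 548 days. That is not so, because subjects under 18 months use time since birth. A reader might also infer a clean contrast with a post-UX007 side based on days actually observed. The SAP supports this only in part. Early terminators' events are counted to the termination visit, but SAP 5.11 runs ongoing subjects to the data cutoff, and 8.5.4.1 does not separately state the 18-month post denominator.

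A fair warning concerns the remedy. If coverage is taken to start at the first record found, that record may itself be an event. One admission 6 months before UX007 would then give 1/(182.6/365.25) = 2.0 per year instead of 1/(548/365.25) = 0.67, which inflates the pre rate in favour of UX007. This stands, and it determines how the start of coverage must be defined.

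**Conclusion.** The rule is wrong as written for subjects aged 18 months or more whose records cover fewer than 548 days. For them the pre-UX007 rate is understated by covered days/548: 0.67 at 12 months, 0.50 at 9 and 0.33 at 6. The direction is toward no effect, so the error would not flatter UX007.

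The size for the cohort is unknown. The number of short-record subjects is not stated and may be zero, in which case there is no bias; the cohort ratios above are illustrations. They assume a constant event rate over the window and equal true rates in subjects with short and full records.

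A reader might conclude that the main efficacy result is compromised. The documents do not support this: the primary analysis (SAP 8.5.1) is descriptive over study period 1 and uses no pre-UX007 rate. The point concerns the supplementary pre/post MCE analyses, mainly in the naïve cohort. It should be corrected because the principle is already applied to infants and the change is small.

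**What to change.** 1. In SAP 8.5.4.1 and 8.5.5.1, take as the pre-period denominator the days within the 548-day window that the subject's records cover, keeping the birth-date rule. Define the start of coverage independently of any event: the date from which the site confirms that the event history is complete, not the date of the first recorded event. Carry the definition into 5.10.3 so that the sections agree.

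2. Report the fixed-548-day result alongside, and add a sensitivity analysis restricted to subjects with full 548-day coverage, or coverage since birth.

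3. In SAP 8.5.4.2.1 and 8.5.5.2.1, state that the offset is log(pre-period days) for the pre row and log(post-period days) for the post row.

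The cost is SAP wording plus one coverage date per subject confirmed from source. The documents describe no field for that date, so some records may need a second look. Subjects with short coverage will have noisier pre rates. If coverage proves complete, the pre-UX007 annualized rates do not change and the assumption is documented.
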